11.5 Sample Size and Power

For the primary outcome death/failure of the intervention, we conduct two parallel studies: (i) VENT versus control UC, (ii) HPS versus control UC. Approximately 128 children will be enrolled in the studies. This includes the 64 children in UC comprised of 16 randomized to UC in the 2018-2019 malaria seasons and augmented by 48 historical controls from previous seasons (2014-2017). We also randomized 16 children to VENT in the 2018-2019 malaria seasons.

Table 8: Summary of outcome measures and analytic plan		
Outcome measure	Outcome type/scale	Analytic method
PRIMARY OUTCOME		
Success of primary intervention or survival in the first 7 days after randomization	Binary	Logistic regression
SECONDARY OUTCOMES		
Brain volume determination (MRI on admission, then daily)	Ordinal	Ordinal regression
Optic Nerve Sheath Diameter (on admission, then daily)	Continuous	Linear regression. Serial assessments by repeated measures analysis
Transcranial Doppler ultrasound (on admission, then daily)	Continuous	Linear regression. Serial assessments by repeated measures analysis
Opening CSF pressure (mm CSF) (on admission)	Continuous	Linear regression
Heart rate variability patterns	Continuous	Linear regression. Serial assessments by repeated measures analysis
Neurologic exam * (on admission, then twice daily)	21 binary and 5 continuous variables	Linear or logistic regression
Papilledema (on admission, then daily)	Binary	Logistic regression
Severe neurologic sequelae at 16 and 12 months	Binary	Logistic regression. Serial assessments by repeated measures analysis
Hypotension that occurs within 30 minutes of sedation administration, initiation of mechanical ventilation or ventilator pressure adjustment.	Binary	Logistic regression.

Since the beginning of this study, we faced several logistical challenges but had success in recruiting 32 children in 2018-2019 (16 each in VENT and UC). Based on our current data, the estimated mortality in UC and VENT are respectively, 36% and 25%. Maintaining the mortality rate in UC, a one-sample lower test at significance level $\alpha=0.05$ of a null difference has 80% power to detect a reduction in mortality to 18% in VENT with 33 subjects in VENT.

[figure not shown]

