Variable	OS mean	OS SD	TBS mean	TBS SD	P value
Age (months)	48.25	27.54	59.63	27.88	0.168
Glucose	5.87	2.94	5.63	3.13	0.914 ^d
Hematocrit (%)	23.36 ^a	6.29	25.54	6.97	0.555 ^d
Platelets (*1000/MicroL)	148.9 ^b	373.7	94.3 ^c	176.2	0.993 ^d

OS= observational study (n=48), SD= standard deviation, TBS= treating brain swelling clinical trial (n=16)

^a n=45, ^b n=47, ^c n=15. ^d nonparametric test.

There was no significant difference in admission Blantyre Coma score (p=0.948), sex (p=0.885) or outcome (death/survival, p=0.551) between the 48 children in the observational study and the 16 randomized participants in the Treating Brain Swelling clinical trial.

We therefore conclude that participants enrolled in the observational study (n=48) are comparable to participants randomized to Usual Care (n=16) in the Treating Brain Swelling clinical trial.

We anticipate enrollment in the Usual Care arm in the 2023 season (see below) at a reduced ratio compared to the intervention arms.

Possible future declaration of futility of the ventilation arm:

If we combine the mortality risk in Historical Controls and participants already randomized to Usual Care, the mortality risk of the combined historical control group and children randomized to Usual Care is 36%. At the end of the 2021 season, the mortality risk in the VENT arm was 26.3%. (Five of 19 participants randomized to VENT died or were brain dead.) With only these data, the test of the null hypothesis of a null difference in mortality is not significant (p-value 0.818, 2-sided test).

We believe it likely that VENT will, in the future, be declared futile. If so, randomization of participants enrolled in the Treating Brain Swelling clinical trial after the declaration of futility of VENT would be to HPS or UC. A formal approach to futility assessment for VENT is provided below.

Table 4. Projected enrollment

	2018 – 2021	2022	2023	Total
*Usual care (UC)	64	0	4	68
Ventilatory support (VENT)	19	7	6	32
Hypertonic saline (HPS)	3	14	15	32

*historical controls + study participants enrolled in 2018 and 2019.

Assuming that enrollment in 2023 follows the same trend seen since the beginning of the clinical trial, we will be able to detect a 50% or more risk reduction in either the VENT or HPS arms, compared to UC.

Choice of interventions

The three study arms of the study will be:

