11.6 Interim Analyses

The TBS design is a 4-stage sequential plan to compare VENT to UC on the outcome of mortality. Based on historical controls and initial randomization to UC before 2020, mortality is

assumed fixed at $p_0 = 0.28$. We test the hypothesis that mortality p in VENT is lower, i.e., we test $H_0 : p = p_0$ versus $H_1 : p < p_0$ at significance level $\alpha = .05$. VENT will be declared superior to UC, if we can demonstrate a relative risk reduction of 50% with 80% power. This needs a sample of 38 subjects.

Boundaries for the 4-stage plan are derived from the power family. Early stopping is to reject the null hypothesis. Our first interim analysis was conducted with data from the 2019-2020 malaria seasons. Observed mortality in VENT was 12.5% (2/16). The conclusion was to continue to the next stage. Our current estimate, at the end of the 2021 season is 15.8% (3/19). In accordance with the design, we must continue to the next stage (i.e., 2022 season). The revised boundary information is depicted in the figure.

Figure: Boundary plot at conclusion of stage 2

Legend: The scale is the maximum likelihood estimate (MLE) of the mortality difference (PDIFF), $\theta = p - p_0$ against the actual information level. At stage 1, observed $\theta = 0.125 - 0.28 = -0.155$, and at stage 2, $\theta = 0.158 - 0.28 = -0.122$. The rejection boundaries are not crossed.

Conditional power and predictive power

Conditional power (CP) is the power to reject the null hypothesis $H_0: \theta = 0$ at all future stages given the cumulative interim data. This calculation shows: (a) at the current estimated difference in mortality $\theta = -0.122$, CP=76.1%, (b) at zero difference in mortality, CP=18.6%, (c) at the hypothesized difference, $\theta = -0.14$, CP=82.9%. Predictive power (PP) is the posterior probability

of rejecting the null at the next stage given the current data, assuming a non-informative prior on the mortality difference. PP=66.1% at the current stage.

Based on these assessments it behooves that we proceed to stage 3.

Hypertonic saline (HPS) vs UC

We have our first sample of 3 subjects, one of whom died. Although hardly necessary, a formal analysis provides the exact 95% CI for mortality in HPS, (0.008, 0.906).

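### Section 11.5 claims 80% power with 33 VENT children without naming the test; by enumeration, rules at or near the 5% level give 62% to 77%

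*Combined protocol and SAP*

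**What the plan says.** Section 11.5 (Sample Size and Power) describes "a one-sample lower test at significance level $\alpha=0.05$ of a null difference". The control rate is taken as known ("Maintaining the mortality rate in UC") at 36%. The claim is that this test "has 80% power to detect a reduction in mortality to 18% in VENT with 33 subjects in VENT". The section does not say whether the test is exact, score or Wald, which variance is used, whether a continuity correction applies, or whether 33 allows for interim looks.

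Section 11.6 plans the same comparison with other inputs: control mortality 28%, a 50% relative reduction, alpha 0.05 and 80% power. It adds "This needs a sample of 38 subjects" and "Boundaries for the 4-stage plan are derived from the power family".

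The projected-enrolment table in Section 4 (Study Design) ends with 32 children in VENT. The text below it says that, if enrolment follows the trend, "we will be able to detect a 50% or more risk reduction in either the VENT or HPS arms, compared to UC".

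**The concern.** For 36% against 18% on a one-sided 5% test, 33 subjects is low for 80% power. The usual score formula asks for 39. Section 11.6 needs 38 for a halving from a different control rate, and its formula does not give 33 when moved to 36%. Because the number of deaths among 33 children is a small integer, normal approximations can differ visibly from the power actually achieved.

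What is at stake is how the projected 32 VENT children are read. The 33/80% sentence puts 80% power one child above that projection, whereas the 38 in Section 11.6 puts it six above. If 80% is not attained at 33, the more reassuring of the two statements should not be relied on.

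**Working it through.** **Inputs (all from Section 11.5).** p0 = 0.36, p1 = 0.18, difference d = 0.18, n = 33, one-sided alpha 0.05 (z = 1.645), power 80% (z = 0.842). Variances: p0(1 − p0) = 0.2304 and p1(1 − p1) = 0.1476. Standard errors at 33: √(0.2304/33) = 0.0836 and √(0.1476/33) = 0.0669.

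**Step 1: trying to reproduce 80% at 33.**

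| Approximation | Power at 33 | N for 80% |
|---|---|---|
| Alternative variance: Φ(0.18/0.0669 − 1.645) = Φ(1.047) | 85.2% | (1.645 + 0.842)² × 0.1476/0.18² = 28.2, so 29 |
| Same, continuity correction 1/(2n) = 0.0152: Φ(0.820) | 79.4% | 33.5 |
| Alternative variance, four-stage Pocock-type inflation 1.14 to 1.22 | about 78% to 81% | about 32 to 34 |
| Alternative variance, four-stage O'Brien-Fleming-type inflation 1.03 | 84% | 29 |
| Score: Φ((0.18 − 1.645 × 0.0836)/0.0669) = Φ(0.636) | 73.8% | 38.2, so 39 |
| Arcsine | 76.3% | 36.7, so 37 |
| Null variance throughout | 69.5% | 44.0 |

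The stated pair is therefore recoverable to within about 2 points by the second or third row, but Section 11.5 mentions neither adjustment.

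**Step 2: does one method give both 33 and 38?** For the inputs of Section 11.6 (0.28 against 0.14), the uncorrected alternative-variance formula gives (1.645 + 0.842)² × 0.1204/0.14² = 37.98, which is the stated 38. The same formula gives 29, not 33, in Section 11.5. The two variants that come near 33 here give about 45 (continuity correction) and 43 to 46 (Pocock-type inflation) in Section 11.6. No variant tried yields both.

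**Step 3: enumeration at n = 33.** With X deaths, size = P(X ≤ c | 33, 0.36) and power = P(X ≤ c | 33, 0.18).

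| Reject at | Size | Power | Score z at c | Wald z at c |
|---|---|---|---|---|
| ≤ 6 | 2.2% | 61.7% | −2.13 | −2.65 |
| ≤ 7 | 5.2% | 76.8% | −1.77 | −2.08 |
| ≤ 8 | 10.8% | 87.5% | −1.41 | −1.58 |

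The exact level-0.05 test rejects at ≤ 6. Both z tests pass −1.645 at 7 deaths and fail at 8, so both reject at ≤ 7, with true power 76.8%. The 73.8% score value in Step 1 is a normal approximation to this same rule. The first cut above 80% has a size of about 11%.

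**Step 4: at the projected 32 and beyond.** At n = 32, rejecting at ≤ 6 has size 2.8% and power 64.9%; rejecting at ≤ 7 has size 6.6% and power 79.4%. Exact power is not monotone in n because the cut moves in whole deaths: 71.2% at 30, 68.1% at 31, 64.9% at 32, 61.7% at 33, 74.1% at 34. The exact test first reaches 80% at n = 40 (≤ 9 deaths, size 4.97%, power 83.0%). It falls below 80% at 42 and 43, and stays above at every n checked from 44 to 55.

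**The case against.** The strongest defence is that Section 11.5 names no test, so a reviewer who picks the exact or score form is testing something that the plan did not promise. About 80% can be recovered with the variance that also produces the 38 in Section 11.6. The interim boundaries are drawn on the estimated mortality difference against information, which points to a normal-theory test, and for such a test the shortfall at 33 is about 3 points. The exact 62% sits at a low point of the sawtooth. The primary test is tied in Section 11.7 to the sequential design of Section 11.6, so the 33 does not drive the analysis. A figure that follows the power sentence is also not available in the text reviewed and might bear on the method.

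Much of this stands. A reader might infer that the plan's arithmetic is simply wrong, or that the test it names delivers only 62% to 74%. The documents support neither: no form is named, approximations near 80% exist, and the z-test rule has 77%. Nor is the 33/80% sentence the only support for 32 VENT children, since Section 4 makes its own detectability claim without citing it.

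The defence does not rescue the figure itself. The adjustments that come near 80% are unstated and do not carry over to the 38. An approximation near 80% also does not give the rejection rule 80% power: enumeration depends only on the inputs in Section 11.5, and no rule at or near 5% gets there.

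**Conclusion.** The point holds in this form: Section 11.5 states a power that its own inputs do not deliver and does not say how the figure was obtained. At n = 33 the power is 62% for a valid exact level-0.05 test (18 points below the statement), or 77% for the Wald or score z test (3 points below, with actual size 5.2%). Which of these applies depends on a choice that the plan has not recorded. The method behind the 33 cannot be identified from the text.

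These figures assume a single look, 36% control mortality treated as known, and a true VENT rate of 18%. Treating the control rate as known is a separate matter: a two-sample one-sided comparison of 33 VENT with 64 UC children would have about 58% power.

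It would go too far to conclude that the trial must enrol more children. The finding concerns a stated figure, which should be corrected and should not be used to support the projected enrolment.

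**What to change.** In Section 11.5:

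- Name the form of the test and the variance used, and say whether any continuity correction or sequential inflation is included.
- Replace the 80% with the matching figure at 33: about 62% for the exact level-0.05 test, or about 77% for the z test with its actual size of 5.2%.
- Give the figure at the projected 32: 65% exact at size 2.8%, or 79% for rejection at 7 or fewer deaths at size 6.6%. Note that exact power is not monotone in n, so that the higher value at 32 is not misread.
- State that these are single-look figures with UC mortality treated as known.

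In Section 4, do not rest the claim about a 50% reduction in VENT on the 33/80% statement.

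The cost is a few sentences and a less favourable stated power. No extra patients are needed.

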11.6 Interim Analyses

The TBS design is a 4-stage sequential plan to compare VENT to UC on the outcome of mortality. Based on historical controls and initial randomization to UC before 2020, mortality is

assumed fixed at $p_0 = 0.28$. We test the hypothesis that mortality p in VENT is lower, i.e., we test $H_0 : p = p_0$ versus $H_1 : p < p_0$ at significance level $\alpha = .05$. VENT will be declared superior to UC, if we can demonstrate a relative risk reduction of 50% with 80% power. This needs a sample of 38 subjects.

Boundaries for the 4-stage plan are derived from the power family. Early stopping is to reject the null hypothesis. Our first interim analysis was conducted with data from the 2019-2020 malaria seasons. Observed mortality in VENT was 12.5% (2/16). The conclusion was to continue to the next stage. Our current estimate, at the end of the 2021 season is 15.8% (3/19). In accordance with the design, we must continue to the next stage (i.e., 2022 season). The revised boundary information is depicted in the figure.

Figure: Boundary plot at conclusion of stage 2

Legend: The scale is the maximum likelihood estimate (MLE) of the mortality difference (PDIFF), $\theta = p - p_0$ against the actual information level. At stage 1, observed $\theta = 0.125 - 0.28 = -0.155$, and at stage 2, $\theta = 0.158 - 0.28 = -0.122$. The rejection boundaries are not crossed.

Conditional power and predictive power

Conditional power (CP) is the power to reject the null hypothesis $H_0: \theta = 0$ at all future stages given the cumulative interim data. This calculation shows: (a) at the current estimated difference in mortality $\theta = -0.122$, CP=76.1%, (b) at zero difference in mortality, CP=18.6%, (c) at the hypothesized difference, $\theta = -0.14$, CP=82.9%. Predictive power (PP) is the posterior probability

of rejecting the null at the next stage given the current data, assuming a non-informative prior on the mortality difference. PP=66.1% at the current stage.

Based on these assessments it behooves that we proceed to stage 3.

Hypertonic saline (HPS) vs UC

We have our first sample of 3 subjects, one of whom died. Although hardly necessary, a formal analysis provides the exact 95% CI for mortality in HPS, (0.008, 0.906).

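### The primary VENT test treats usual-care mortality of 0.28 as known, so its 5% level does not apply to a claim of superiority over usual care; separately, 38 VENT children do not give 80% power

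*Combined protocol and SAP*

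**What the plan says.** - **Section 11.6** sets the null value: "Based on historical controls and initial randomization to UC before 2020, mortality is" taken as fixed at 0.28. VENT mortality is tested one-sided at 0.05 in a four-stage plan that stops early only to reject. The reading of a rejection is explicit: "VENT will be declared superior to UC, if we can demonstrate a relative risk reduction of 50% with 80% power". On size: "This needs a sample of 38 subjects". Two looks are complete: "Our first interim analysis was conducted with data from the 2019-2020 malaria seasons" (2/16 deaths), and the 2021 season brought the total to 3/19.
- **Section 11.5** puts UC at 64 children, 16 of them randomised in 2018-2019, "augmented by 48 historical controls from previous seasons (2014-2017"). It holds the UC rate fixed as well, at 36%: "Maintaining the mortality rate in UC, a one-sample lower test at significance level" 0.05 "has 80% power to detect a reduction in mortality to 18% in VENT with 33 subjects in VENT".
- **Section 11.6.1** gives conditional power of 76.1% at the current difference, 82.9% at the design difference and 18.6% at zero. It reads the first two as promising and concludes that the evidence does not point to futility.
- **Section 11.7** sends the primary test to the design in 11.6. **Table 8** instead lists logistic regression for the primary outcome ("Success of primary intervention or survival in the first 7 days after randomization").
- **Section 4** projects 32 VENT and 68 UC children in total, including 4 more UC children in 2023.

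**The concern.** The conclusion compares two groups, but the test allows for chance in only one. The 5% level holds for the hypothesis that VENT mortality equals 28%. It does not hold for the hypothesis that VENT mortality equals UC mortality, because 0.28 is itself an estimate from about 64 children. Any UC child randomised in 2023 cannot affect a test whose null value is already fixed.

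A false claim of superiority would concern early mechanical ventilation of critically ill children. The stated power and conditional power matter too, because they support the decision to continue.

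**Working it through.** **Inputs.** p0 = 0.28, design rate 0.14, one-sided 5%, 38 VENT, 3/19 so far (11.6); 64 UC, and 0.36 to 0.18 with 33 VENT (11.5); 32 VENT and 68 UC projected (Section 4). Assumption: 18/64 UC deaths (0.28 x 64 = 17.9; the count is not printed), exact 95% interval 17.6-40.8%.

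**1. Reproducing the plan.** With the alternative variance for both error terms, n = (1.645 + 0.842)^2 x 0.14 x 0.86 / 0.14^2 = 37.98, so 38. With the null variance 0.28 x 0.72 for the critical value and the alternative variance for power, n = 54.2. The smallest exact n with size at most 5% and power at least 80% is 57. The conditional powers reproduce within a point (76.0 / 82.7 / 18.5%), using the alternative variance for the maximum information, the observed variance at stage 2, late-spending boundaries, and no error in p0.

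**2. Type I error for the claim against UC.** If p0 is estimated from 64 children and then held fixed, the variance of the difference is (1 + n/64) times what the test assumes. The error is 1 - Phi(1.645 / sqrt(1 + n/64)):
- n = 32: 9.0%
- n = 38: 9.6%

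Exact enumeration over UC deaths ~ Bin(64, p) and VENT deaths ~ Bin(n, p), for n = 32 or 38 and p = 0.28 or 0.36, with the cut-off re-derived for each UC count:

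| Rule | Averaged error |
|---|---|
| Exact binomial | 6.4-7.5% |
| Null-variance z | 8.1-9.3% |
| Estimated-variance z | 10.5-11.6% |
| Two-sample pooled z (32 or 38 vs 64) | 4.7-5.1% |

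**3. The constant 0.28 itself.** Chance of rejecting with an ineffective VENT arm, by true UC mortality (binomial distribution function at n = 38):

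| Cut-off | 18% | 22% | 28% | 36% | 41% |
|---|---|---|---|---|---|
| 5/38 | 30% | 13% | 2.6% | 0.2% | 0.02% |
| 6/38 | 46% | 24% | 6.2% | 0.5% | 0.1% |

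**4. Power with p0 truly known (plan: 80%).**
- 0.28 to 0.14, n = 38: cut-off 5 gives 56% (size 2.6%); cut-off 6 gives 72% (size 6.2%).
- 0.36 to 0.18, n = 33: cut-off 6 gives 62% (size 2.2%); cut-off 7 gives 77% (size 5.2%).

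If p0 is instead estimated from 64 children and plugged in, average power at n = 38 (0.28 to 0.14) is 56% (exact), 63% (null variance) or 70% (estimated variance). Ignoring UC error therefore inflates the error rate; it is not what lowers the planned test's power.

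**5. Power of a valid two-sample comparison with UC** (pooled z, full enumeration):

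| VENT vs UC | 0.28 to 0.14 | 0.36 to 0.18 |
|---|---|---|
| 32 vs 64 | 46% | 58% |
| 33 vs 64 | 47% | 59% |
| 38 vs 64 | 50% | 63% |

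**6. Conditional power from 3/19.** One final look at 38 is assumed, because the boundary parameter and figure are not in the text. With cut-off c, it is P(Bin(19, p) <= c - 3):

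| | p = 0.158 | p = 0.14 | p = 0.28 |
|---|---|---|---|
| Plan | 76.1% | 82.9% | 18.6% |
| c = 6 | 65% | 73% | 18% |
| c = 5 | 40% | 49% | 7% |

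Cut-off 5 is where an exact one-sample 5% rule stops. It is also where the two-sample test stops given 18/64: z = -1.75 at 5/38 and -1.42 at 6/38. The null-variance one-sample z still rejects at 6/38 (z = -1.68).

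**The case against.** **The design is disclosed.** Sections 11.5 and 11.6 openly describe a one-sample test with a fixed UC rate, and against a 28% benchmark its level is nominally valid. That stands; only the reading of a rejection as superiority over UC fails.

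**Table 8 lists logistic regression, which would carry UC error.** It does not rescue the plan, because 11.7 sends the primary test to 11.6 and offers Table 8 for the secondary outcomes. At best the plan names two primary analyses.

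**Changing the primary test after two looks in an unmasked trial has its own cost**, and 48 of the 64 controls would still be non-concurrent. This stands, so a change of test should not be the only acceptable remedy.

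Four stronger readings are tempting but unsupported:
- A reader might infer that UC sampling error explains the fall from 80% to 50% power. The 50% belongs to a different, two-sample test. The planned test's shortfall comes from the sample-size formula and discreteness. On conditional power, the exact one-sample and two-sample rules share the same cut-off, so UC error adds nothing identifiable there.
- A reader might quote 46% as the false-positive rate. That puts true UC mortality at the edge of the interval for an assumed 18/64 and uses a cut-off whose size is already 6.2%.
- A reader might take 36% as proof that 0.28 is wrong. VENT shows a similar split: 3/19 in 11.6, but 5/19 dead or brain dead in Section 4. The two UC figures may describe different endpoints, although Section 4 labels its figure mortality.
- A reader might conclude that VENT should have been called futile. The lower conditional powers do not require that.

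**Conclusion.** The point holds in three parts.

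1. **Error.** As a claim against UC, the nominal 5% is about 6-12% averaged over the sampling of 64 controls. For the constant 0.28, the error is above 5% if true UC mortality is clearly lower and below 5% if it is higher. The documents do not settle which applies.
2. **Power, a separate defect.** 80% is not reached even with p0 known: 56% or 72% at 38 VENT, and 62% or 77% for the second claim at 33 VENT. The formula defect is small in that second case near 5% size.
3. **Conditional power.** 76.1% and 82.9% are too high: 65% and 73%, or 40% and 49%, by cut-off.

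These figures assume 64 controls exchangeable with the trial children; the conditional powers also assume a single final look at 38, and the two-sample cut-off assumes 18 UC deaths. Drift since 2014-2017 is not in them. The superiority wording and the 80% statements must be corrected before the final analysis.

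**What to change.** In either case:
- Restate power, conditional power and predictive power by exact or null-variance methods.
- Reconcile 11.7 with Table 8, so that one primary analysis is named.
- State which endpoint each UC figure uses (28% may be death; 36% may be death or brain death).

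Then choose one:

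**(a) Two-sample comparison.** Make the arm comparison already in Table 8 and 11.7 primary, entering all UC children as data, including any from 2023. Recompute the remaining boundaries and state, through the DSMB, how the two completed looks (2/16 and 3/19) are counted. Quote power of about 46-50% (0.28 to 0.14) or 58-63% (0.36 to 0.18).

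**(b) Benchmark.** Keep the one-sample test, word its conclusion as against a 28% benchmark and not as superiority over UC, give its exact cut-off, size and power, and show sensitivity over p0 of about 18-41%.

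Option (a) costs an SAP amendment, DSMB review and a less favourable power figure. Option (b) costs wording, the recalculated figures and a sensitivity table. Neither needs extra patients. By normal theory, restoring 80% two-sample power against 64 UC would take about 212 VENT children (0.28 to 0.14) or 86 (0.36 to 0.18), so restating power is the realistic course. Under either option, the plan should say that drift in the historical controls remains.

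### Section 11.6 needs 38 VENT subjects for 80% power, but 32 are projected, where the same formula gives about 74% before interim looks; the 28% and 36% control rates are not reconciled

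*Combined protocol and SAP*

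**What the plan says.** Section 11.6 describes a four-stage, one-sample comparison of VENT mortality with a control rate fixed at 0.28. It is one-sided at 0.05, with power-family boundaries and early stopping only to reject the null. For 80% power to show a 50% relative reduction it says "This needs a sample of 38 subjects". Section 11.7 takes the primary test from this design.

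Section 4 gives a different size. Under "Table 4. Projected enrollment" (the second table numbered 4) the VENT row is 19, 7 and 6, total 32. The text below the table says that, on current trends, "we will be able to detect a 50% or more risk reduction in either the VENT or HPS arms, compared to UC". Section 11.5 says "Approximately 128 children will be enrolled in the studies", which fits 64 UC + 32 HPS + 32 VENT. The table itself sums to 68 + 32 + 32 = 132, because its UC row is 68.

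Section 11.5 has a separate calculation, from 36% to 18%, which "has 80% power to detect a reduction in mortality to 18% in VENT with 33 subjects in VENT".

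The rates also differ (percentages in both quotes). Section 4 says "the mortality risk of the combined historical control group and children randomized to Usual Care is 36", and Section 11.5 says "the estimated mortality in UC and VENT are respectively, 36% and 25". Section 11.6 draws on the same two control sources and uses 28%; for VENT it gives 2/16 (12.5%) and later 3/19 (15.8%). Section 4 says "Five of 19 participants randomized to VENT died or were brain dead" (26.3%).

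**The concern.** A reader, or the DSMB, will take the primary VENT comparison as having 80% power against a halving of mortality. On the plan's own projection it does not, if 28% is the right control rate. A non-significant VENT result would then be weaker evidence against benefit than the text implies.

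The two control rates decide how large the problem is, and the plan does not say which belongs to the primary endpoint. They also change the picture at the second look. The difference is 3/19 − 0.28 = −0.122 on the 11.6 figures and 5/19 − 0.36 = −0.097 on the Section 4 figures.

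**Working it through.** **Inputs.** Section 11.6: p0 = 0.28, p1 = 0.14, one-sided alpha 0.05, power 0.80, four looks. Section 4: 32 VENT subjects. Section 11.5: 36% to 18%, 33 subjects. p0 is treated as a known constant throughout, as in the plan.

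**1. Reproducing 38.** One look, variance at the alternative (0.14 × 0.86 = 0.1204):

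n = (1.645 + 0.842)² × 0.1204 / 0.14² = 37.98, so 38.

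With the critical value at the null variance the answer is 54.2; with the null variance throughout it is 63.6; two-sided with the alternative variance it is 48.2. Only the first form gives 38.

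**2. The same formula at 32.** Power = Φ(0.14 × √32 / √0.1204 − 1.645) = 73.8%. At 38 it is 80.0%.

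**3. Four looks.** Boundaries are Z_k = C × t_k^(shape − 0.5), with C solved for an overall one-sided 0.05 and variance 0.1204. The text does not state the shape, so 0 to 0.5 is an assumed range.

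| Shape | n = 32, equal looks | n = 32, looks at 16/19/26/32 | n = 38, equal looks | Maximum n for 80%, equal looks |
|---|---|---|---|---|
| 0 | 72.5% | 72.2% | 78.8% | 39.3 |
| 0.25 | 70.6% | 70.7% | 77.1% | 41.2 |
| 0.5 | 65.4% | 68.1% | 72.2% | 46.5 |

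**4. Splitting the loss.** Going from 38 to 32 costs 80.0 − 73.8 = 6.2 points with one look. With four equal looks it costs 78.8 − 72.5 = 6.3 (shape 0) to 72.2 − 65.4 = 6.8 (shape 0.5). The remaining loss comes from interim looks and is present at 38 as well.

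**5. The 36% rate.** The formula of step 1 gives n = 28.16 for 36% to 18%. Power at 32 is 84.3% with one look and 77-83% with four. The stated 33 is not reproduced with one look (29 alternative variance, 39 score, 40 exact). Four-look inflation at shape about 0.4 gives 32.5, but that shape would turn 38 into 44. So 33 and 38 do not appear to treat the interim looks in the same way.

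**6. Counts behind the rates.** On 64 controls, 36% is about 23 and 28% about 18. For VENT, 25% of 16 is 4 against 2/16, and later 5/19 against 3/19. The VENT gap is two children both times, which would fit two different endpoints.

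**7. Conditional power.** The reported values at θ = −0.122, 0 and −0.14 are 76.1%, 18.6% and 82.9%. They are reproduced within 0.2 point by a maximum of 42 with shape 0.25 (variance 0.1204), and within 0.5 point by maxima of 40 or 44 with shape 0 under other variance choices. These set-ups are inferred, and the maximum is not identified. With stages at 26 and 32 instead, the same three set-ups give 61.5-66.7% at −0.122 and 67.9-73.5% at −0.14.

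**The case against.** - **The 32 is a projection.** Section 11.7 says arm sizes will vary. That is true, but Section 4 attaches its detectability claim to that projection, so the power there should be stated.
- **The Section 4 sentence is consistent with its own section.** It sits beside a 36% control rate, at which 32 subjects give 84% (one look) or 77-83% (four looks). This stands. A reader might infer that the sentence is wrong and should go; it conflicts only if 28% applies.
- **The plan signals different endpoints.** Section 11.5 speaks of death or failure of the intervention, Section 4 of death or brain death, and Section 11.6 of mortality. This is a likely explanation. But only the 5/19 count is spelled out as including brain death, the 26.3% it supports is itself introduced as a mortality risk, and both control rates are called mortality. Nothing in the text reconciles them. Nor do the documents establish the stronger inference that the interim looks used the wrong endpoint.
- **The boundary shape may be in the plan.** Section 11.6 refers to a boundary plot that was not available for this check. It may show the shape and information levels, so their absence from the text is not counted as an omission. The low end of the range needs shape 0.5, which fits the reported conditional powers poorly: with variance 0.1204 and maxima of 38 to 44 it gives 64-71%, 14-15% and 72-79%.
- **Power could be read as lower still.** One-look score and exact tests at 32 give 56% and 53%. These show sensitivity to the choice of test. They are not a range for the four-stage power, and the plan does not name either test.

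**Conclusion.** The point holds as an inconsistency in the stated power. Under 11.6's own assumptions the projected 32 VENT subjects give about 74% by the formula that reproduces 38, before interim looks. Under the four-stage plan they give about 71-72% for shapes 0 to 0.25, or down to 65% at shape 0.5. The one-look figure needs no assumption about shape; the four-look figures do, and all use the alternative variance and a known control rate.

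A reader might put the whole drop from 80% to 65% down to enrolment. Only 6-7 points come from it; even at 38, four equal looks give about 72-79%. Nor does this overturn the decision to continue: the conditional powers recomputed at a maximum of 32 for the observed and hypothesized differences stay well above the 20% guide in Section 11.6.1.

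The 36% and 28% control rates, and the paired VENT figures, remain unreconciled. Because power at 32 is 84% on one rate and 74% on the other (one look), this has to be settled before either power statement can be relied on.

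**What to change.** 1. In Sections 4, 11.5 and 11.6, label each rate (36% and 28%; 25% of 16 and 2/16; 5/19 and 3/19) with its endpoint and counts, and say which is the primary endpoint. Leave p0, the completed looks and the boundaries unchanged.
2. In 11.6, keep 38 as the design size and add: *Projected VENT enrolment is 32. By the formula behind 38, power for 28% to 14% at 32 is about 74% before interim looks; under the four-stage plan it is [value from the sponsor's program].* Our estimate of that value is about 65-72%. State whether 38 and 33 include inflation for four looks.
3. In 11.6 and 11.6.1, give the maximum sample size behind the reported conditional powers, and report them also at a maximum of 32.
4. In Section 4, qualify the sentence on detecting a 50% reduction with the control rate and power that it assumes. It need not be removed.

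The cost is recalculation, rewording of four sections and a less favourable stated power. No extra enrolment is needed.
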